## 12 Previous or Concomitant Medications/Procedures

**Concomitant treatments** are medications, other than study medications, which are taken by subjects any time during the study (on or after the first day of study drug treatment for each subject) or within 30 days after last dose of study drug.

Concomitant treatment will be summarized from the “Concomitant Medications” CRF page. ATC-2nd level and preferred term will be tabulated as given from the WHO-DD dictionary current version. In case multiple ATCs are assigned to a drug, all ATC-2nd levels will be used for reporting. In case the date values will not allow unequivocal categorization of a medication as concomitant, the medication will be considered as concomitant medication.

**Previous medications** are medications, other than study medications and premedications for study drug, which started before first administration of study drug.

Previous treatment will be summarized from the “Relevant Previous Medications” CRF page. ATC-2nd level and preferred term will be tabulated as given from the WHO-DD dictionary current version. In case multiple ATCs are assigned to a drug, all ATC-2nd level will be used for reporting. In case the date values will not allow unequivocal categorization of a medication as previous, the medication will be considered as previous medication.

All reported previous medications will be listed.

**All concomitant procedures**, which were undertaken at any time during the study, will be summarized according to the CRF page “Concomitant Procedures”. Concomitant procedures will be classified by medical review.

The number of subjects with concomitant procedures overall and by type of procedure (as classified by medical review) will be tabulated.

All relevant concomitant medication and procedure data will be listed.

## 13 Treatment Compliance and Exposure

All dosing calculations and summaries will be based on the "M4112 Administration Details" CRF page. The Safety Analysis Set will be used for these analyses.

Handling of missing data:

- If the total actual dose is missing, the planned dose level as entered in the CRF will be used.
- In case the last medication end date is incomplete, the date of M4112 administration will be taken from the "M4112 Termination" page.

The duration of therapy (in weeks) is defined as:

$$\text{Duration} = [(\text{date of last dose} - \text{date of first dose}) + 1] / 7$$

The cumulative dose of M4112 (in mg) is defined as:

$$\text{Cumulative dose (mg)} = [(\text{tablets dispensed}) - (\text{tablets returned})] * \text{dose level (mg)}$$

(Summed over all dose levels taken by the subject, if dosing changes occurred.)

Dose intensity (mg/week) will be calculated as follows:

$$\text{Dose intensity (mg/week)} = \left( \frac{\text{Total cumulative dose of M4112 (mg)}}{\text{Duration of therapy (weeks)}} \right)$$

The relative dose intensity (%) is defined as the dose intensity divided by the planned cumulative dose per cycle, calculated as follows:

$$\text{Relative dose intensity (\%)} = \left( \frac{\text{Total cumulative dose of M4112 (mg)}}{\text{Total planned dose of M4112 (mg)}} \right) * 100\%$$

The following summary tables by dose group and overall will be provided:

- Duration of therapy (weeks)
- Total number of doses taken overall
- Cumulative dose (mg)
- Dose intensity (mg/week)
- Relative dose intensity (%)
- Dose adjustments and missed doses

A listing of treatment exposure and compliance will also be created to summarize the relevant information for each subject:

- Cycle and day in cycle
- Date and time of administration
- Actual dose

- Whether dose has been adjusted, and if yes, reason why
- Reason for no dose (if applicable)

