Prespecified ascending doses of 100, 200, 400, 600, 800, and 900 mg BID (means respectively, 100 mg BID for 200 mg total daily dose, 200 mg BID for 400 mg total daily dose, 400 mg BID for 800 mg total daily dose, 600 mg BID for 1,200 mg total daily dose, 800 mg BID for 1,600 mg total daily dose, 900 mg BID for 1,800 mg total daily dose) as single agent in 28-day cycles are foreseen. Dose escalation decisions will be driven primarily by DLT, safety, and tolerability. **CCI**

A BID dosing regimen will be followed, based on PK modelling, to achieve the target  $C_{min}$  over the dosing interval at a lower total daily dose and thereby reducing  $C_{max}$  and AUC over the day to potentially improve safety and tolerability when compared to once daily (QD) dosing. Based on PK data from subjects, the SMC will evaluate whether this regimen can be sustained or needs to be changed.

In principle, dose escalation of single agent M4112 (Part IA) will proceed according to the recommendation of the SMC to at least the upper end of the above given dose range, unless the MTD has been reached or there is excess of PK nonlinearity, or the SMC recommends to end dose escalation following review of safety, tolerability, PK and PD results. Depending on the observed toxicity profile and available PK and PD, a dose regimen different to or dose(s) higher/lower than the prespecified doses may be tested.

CCI

- CCI

- CCI

CCI

The starting dose of M4112 CCI will be dependent on the observed safety, tolerability, and PK/PD profile during dose escalation in the single agent cohort (Part IA) and will lag at least 1 dose level behind the last completed safe dose level of M4112 as single agent, which was confirmed as safe by the SMC. CCI

CCI

CCI

CCI

CCI

100

CCI

- CCI
- CCI

CCI

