### M4112

M4112 will be packaged in child resistant and tamper sealed wallets. Each wallet will contain 1 blister with 4 tablets of 25 mg or 200 mg M4112 tablets.

All IMPs will be packaged and labeled in accordance with all applicable regulatory requirements and Good Manufacturing Practice Guidelines. All IMPs will be shipped in suitable transport containers according to each IMP's storage and shipping conditions. Shipments are monitored with temperature control devices.

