### 15.1 Dose Limiting Toxicities

The occurrence of dose limiting toxicities (DLTs) during the DLT evaluation period (i.e., during the first treatment cycle of 28 days) is a primary endpoint of this study. The DLT set will be used for the analysis of the primary endpoint. Please refer to [Section 6.2.4](#) of the Clinical Study Protocol MS201408-0005 for the detailed definition of a DLT.

The number and proportion of subjects experiencing DLTs will be reported by dose level. Posterior probabilities (2.5%, 25%, 50%, 75%, and 97.5% quantiles) for a DLT by tested dose level will be estimated using the BLRM specified in the protocol.

Details of the DLTs will be presented in a listing sorted by SOC and PT, including: DLT, SOC, PT, relationship to M4112, seriousness, dose group, time since last and first administration of M4112, and subject's age/sex/site of primary tumor.

In addition, a DLT profile plot of all subjects in the Safety Analysis Set will be produced. This will show a closed square for all subjects who were considered evaluable (in DLT set) and did not have a DLT during Cycle 1, an open square for those who experienced a DLT during Cycle 1, and an open circle for those who were excluded from the DLT Set. This plot will have Cohort Number on the x-axis and dose level (mg) on the y-axis.

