## Appendices

### 18.1 Protocol Deviations Identified by Programming and Clinically Important Events

Inclusion and exclusion criteria are referenced according to Protocol MS201408-0005 version 2.0 dated 08-Sep-2017.

	Description	Code	Clinically Important?	Protocol Section	Proposed Check / Comment
Inclusion / Exclusion Criteria					
Violated eligibility criteria	Any "no" response to inclusion criteria and/or any "yes" response to exclusion criteria, and subject was subsequently entered into the study	INCEXC01			Violations should be documented on the Study Entry CRF page, which is mapped to the IE domain in SDTM
Informed Consent / Subject Information					
Late ICF signature	ICF was signed after study procedure was done	INFCON03			Check that no dates are prior to ICF date
Investigational Product					
Overdose	Subject received $\geq 110\%$ of the calculated dose for that particular administration	INVPR06			Flag if relative dose intensity $\geq 1.10$
Pharmacokinetics-Related					
Vomiting	Vomiting immediately following oral dosing that can affect a PK result	PK001			Manual check by PK scientist
Sample processing errors	Errors that lead to inaccurate bioanalytical results	PK002			Manual check by PK scientist
Inaccurate dosing, dose reductions, dose errors, missed doses	Inaccurate dosing, dose reductions, dose errors, or missed doses that can affect the PK results on one or more PK days	PK003			Manual check by PK scientist

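### The cumulative-dose formula multiplies tablets by dose level instead of tablet strength, and the overdose check tests whole-treatment dose intensity instead of single administrations

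*SAP*

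**What the plan says.** SAP Section 13 obtains cumulative dose in mg by multiplying net tablets (dispensed less returned) by the dose level in mg, with the instruction "Summed over all dose levels taken by the subject, if dosing changes occurred". Dose intensity divides that figure by weeks of therapy. The printed formula for relative dose intensity (RDI) divides it by "Total planned dose of M4112 (mg)", a quantity the section does not define. Cumulative dose, dose intensity and RDI are all to be tabulated by dose group.

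The SAP uses the term dose level for the assigned dose. The missing-data rule in the same section reads "If the total actual dose is missing, the planned dose level as entered in the CRF will be used", and for the DLT profile plot Section 15.1 says "This plot will have Cohort Number on the x-axis and dose level (mg) on the y-axis".

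On supply, Protocol Section 6.6 states "Each wallet will contain 1 blister with 4 tablets of 25 mg or 200 mg M4112 tablets". The Protocol Synopsis gives the planned levels: "Prespecified ascending doses of 100, 200, 400, 600, 800, and 900 mg BID".

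SAP Section 18.1 describes the overdose deviation INVPR06 as at least 110% "of the calculated dose for that particular administration". The programmed check beside it is "Flag if relative dose intensity" at or above 1.10.

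**The concern.** A tablet count becomes milligrams only when multiplied by milligrams per tablet. Multiplying by the assigned dose counts the whole dose once for every tablet in it. The overstatement therefore equals the number of tablets per dose and differs between dose groups, so comparisons of exposure across levels would be distorted, not merely rescaled.

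RDI carries the same error if planned dose is in true mg. INVPR06 would then flag compliant subjects as overdosed at every planned level except 200 mg taken as one tablet. If the milligrams are right, the opposite problem appears: a ratio averaged over all treatment cannot detect most isolated overdoses, although a single administration is what the deviation is defined on.

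**Working it through.** Neither document reports an exposure figure, so there is nothing to reproduce.

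**Inputs**
- Tablet strengths 25 mg and 200 mg (Protocol Section 6.6).
- Planned levels 100 to 900 mg BID (Protocol Synopsis).
- 28-day cycle (Protocol Section 7.1.2), so 2 × 28 = 56 administrations.
- Assumption: dose level means mg per administration.
- Assumption: the tablet mix per dose. No mapping is readable, so two cases are shown: fewest tablets (200 mg first, then 25 mg) and 25 mg tablets only.

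**Overstatement factor**

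Formula mg ÷ true mg = (56 × tablets per dose × dose) ÷ (56 × dose) = tablets per dose. Adherence cancels.

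| Dose (mg BID) | Fewest tablets = factor | True mg per cycle | As-written mg, fewest tablets | Factor, 25 mg only |
|---|---|---|---|---|
| 100 | 4 | 5,600 | 22,400 | 4 |
| 200 | 1 | 11,200 | 11,200 | 8 |
| 400 | 2 | 22,400 | 44,800 | 16 |
| 600 | 3 | 33,600 | 100,800 | 24 |
| 800 | 4 | 44,800 | 179,200 | 32 |
| 900 | 8 (4 × 200 + 4 × 25) | 50,400 | 403,200 | 36 |

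The 100 mg factor is 4 under either mix. Comparing 100 mg with 200 mg:
- Fewest tablets: 22,400 / 11,200 = 2.0, where the true ratio is 5,600 / 11,200 = 0.5. The order reverses.
- 25 mg only: the 200 mg group shows 56 × 8 × 200 = 89,600 mg, so the ratio is 22,400 / 89,600 = 0.25. The order is kept but the gap is wrong.

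**RDI**
- Planned dose in true mg: a fully compliant subject reads 400%, 100%, 200%, 300%, 400% and 800% across the six levels (fewest tablets). At 400 mg, 1.10 × 22,400 / 44,800 = 55% adherence already reaches the overdose threshold.
- Planned dose on the same tablets × dose level basis: the factor cancels and RDI is correct.
- The sentence introducing RDI divides dose intensity by the planned dose per cycle, which is not the printed formula. At 200 mg BID a compliant subject would score 2,800 / 11,200 = 0.25 under that sentence and 1.00 under the formula.
- Section 13 expresses RDI in percent, while Section 18.1 compares it with 1.10.

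**INVPR06 with correct mg and otherwise full compliance**

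One administration at m times the planned dose among n gives RDI = (n + m − 1) / n. This reaches 1.10 only if n ≤ 10(m − 1).

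| Size of single overdose | Flagged only if total administrations ≤ |
|---|---|
| 110% of planned | 1 |
| 1.5 times | 5 |
| Doubled | 10 |
| Tripled | 20 |

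In one 56-dose cycle, one doubled dose gives 57/56 = 1.018, not flagged. Five give 61/56 = 1.089, not flagged. Six give 62/56 = 1.107, flagged. One missed dose offsets one doubled dose: 56/56 = 1.00.

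**The case against.** Section 13 opens by basing all dosing calculations on the M4112 Administration Details CRF page, and Protocol Section 6.9 has the date and dose of each administration recorded. On that view the word tablets is the slip, not dose level: number of doses taken times dose level, summed over levels, gives correct milligrams and fits the parenthetical. That reading is plausible and the documents do not exclude it. It does not rescue the formula, which gives wrong milligrams whichever term is mistaken, but it does bear on the choice of remedy.

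The sizes are conditional. The tablet mix and the levels actually dosed are not readable. The 100/200 mg reversal depends on the mix, and the RDI effects depend on an undefined denominator. If dose level meant total daily dose, the factors would double and 200 mg as one tablet would be overstated twofold. The direction stands regardless, because every planned level other than 200 mg needs more than one tablet.

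The practical weight is limited, and this stands. The outputs are descriptive, in what SAP Section 6 calls an abbreviated final analysis, and no primary endpoint or DLT-model input uses them. A compliant RDI of several hundred percent would probably be noticed before lock. Overdoses are also captured by eCRF entry and expedited report (Protocol Section 6.12), by monitoring and medical review (SAP Section 8.1), partly by the manual PK003 check (SAP Section 18.1), and in the actual-dose listing of Section 13.

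**Conclusion.** Both defects hold as written. With dose level read as mg per administration, following Section 13 literally overstates cumulative dose and dose intensity at least 2-fold to 8-fold at every planned level except 200 mg taken as a single tablet, and by more if additional 25 mg tablets are used. RDI is wrong only if planned dose is in true mg. INVPR06 does not test its own definition: with correct milligrams it needs six doubled doses in an otherwise compliant 56-dose cycle before it flags. Confidence in the formula and check being wrong is high; the exact factors rest on the assumed tablet mix. This should be fixed, but it does not threaten the trial's primary conclusions.

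**What to change.** 1. Cumulative dose: replace dose level with tablet strength, summing (dispensed − returned) × strength over the 25 mg and 200 mg tablets. Alternatively, sum the recorded actual doses, which matches the CRF source named in Section 13, and keep the tablet count as a cross-check. The count is worth keeping. In Cycle 1 only the morning doses on Days 1, 8, 15 and 22 are taken on site, so 52 of 56 doses (93%) are self-administered off site, and a tablet count can reveal an extra dose that was not recorded.
2. Define total planned dose in mg and state how a dose change enters it.
3. Keep the printed RDI formula, delete the adjacent sentence that divides dose intensity by planned dose per cycle, and use one scale (percent or ratio) in Sections 13 and 18.1.
4. Run INVPR06 per administration: recorded dose against the dose planned for that administration, under the existing 110% definition. Keep RDI as a supplementary screen.

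The cost is SAP wording and a few lines of programming. The tablet-strength version needs dispensed and returned counts by strength; the CRF fields are not in the documents, so availability should be confirmed. The per-administration check uses dose records already planned, which for off-site doses depend on what the subject reports. No clinical rule changes.

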## 14 Efficacy Analyses

The Safety Analysis Set will be used for all efficacy analyses, unless otherwise noted. All efficacy endpoints will be listed and summarized descriptively.

### 14.1 Progression Free Survival

Progression free survival (PFS) time, according to RECIST 1.1 as assessed by the Investigator, is defined as the time from first study treatment to the date of the first documentation of objective PD or death due to any cause, whichever occurs first.

PFS data will be censored on the date of the last adequate tumor assessment for patients who do not have an event (PD or death) or for patients with an event after two or more subsequent missing response assessments (i.e., twice the scheduled time interval between two subsequent response assessments – this interval is 8 weeks through Cycle 7, and 12 weeks thereafter). Patients who do not have a baseline tumor assessment or who do not have any postbaseline tumor assessments will be censored at treatment start date unless death occurred on or before the time of the second planned tumor assessment, in which case the death will be considered an event.

Data will be taken from the “Assessment of Disease Based on Imaging” CRF page. The date of the overall response assessment is the earliest date for imaging of target, nontarget, and new lesions taken at that response assessment.

The censoring and event date options to be considered for the PFS analysis are presented in **Table 3**. The last adequate tumor assessment is defined as a tumor assessment with a result other than “NE” or “NA”.

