- u During treatment, CT or MRI scans will be done for tumor assessments within 7 days prior to Day 1 of Cycles 3, 5 and 7 and thereafter every 3 cycles until progressive disease or use of an alternative anticancer therapy. Of note: The method used for baseline assessment must be used for all subsequent assessments. A CT or MRI scan is mandatory to confirm a complete response, partial response and progressive disease at least 4 weeks later.
- v Pretreatment tumor assessment should be performed within 21 + 7 days before the first dose of M4112. A chest X-ray should be performed before a CT or MRI scan to exclude prohibitive entry criteria. CT scans (with contrast media, unless contraindicated) of the chest, abdomen, and pelvis and any other disease sites (eg, neck) should be performed. Alternatively, tumor assessment at Screening can be done by MRI, using the same method at all subsequent assessment time points. Tumor assessment should be continued until confirmed disease progression or stop of study.

CC|

CCI

CCI

t Post corresponds to end of infusion.

CC1  
CC1  
CC1  
CC1

CCI

CCI

CCI

CCI

CCI

CCI

Table 4

**Schedule of Assessments – Pharmacokinetic, Pharmacodynamic, and Electrocardiogram Schedule – Part IA (Dose Escalation – M4112 as Single Agent) – Cycle 1 and Day 1 of Cycle 2**

Cycle/Day	Time points (h postdose) of M4112	PK sampling (blood) a,b	TriPLICATE digital ECG c	CCCI	PK volume for M4112 a (mL)	CCCI	CCCI	Time window (± min b )
Cycle 1 Day:								
1	Predose	X	X e (within 45 min)		4			- 45
1	0.5	X	X c		4			± 5
1	1	X	X c		4			± 5
1	2	X	X c,f		4			± 10
1	3	X	X c,f		4			± 10
1	4	X	X c,f		4			± 10
1	6	X	X c		4			± 10
1	8	X	X c,f		4			± 10
8	Predose d	X	X f (within 30 min)		4			- 30
15	Predose d	X	X e (within 45 min)		4			- 45
15	0.5	X	X c		4			± 5
15	1	X	X c		4			± 5
15	2	X	X c,f		4			± 10
15	3	X	X c,f		4			± 10
15	4	X	X c,f		4			± 10
15	6	X	X c		4			± 10
15	8	X	X c,f		4			± 10
Cycle 2 Day:								
1	Predose d	X	X f (within 30 min)		4			- 30
1	2	X	X f		4			± 10
Total					76			

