### 7.3 Efficacy Assessments

The tumor response assessments will be performed at time points indicated in the Schedule of Assessments (Table 1, Table 2, and Table 3) and as discussed in Section 7.2.5.

- **Clinical endpoints:** Time to tumor response, objective response, best overall response (BOR), DCR, duration of response (DOR), and progression-free survival per Investigator according to RECIST 1.1 (Appendix III). A CT or MRI scan is mandatory for confirming any CR and partial response (PR) after at least 4 weeks following first assessment.
- **Progression Free Survival (PFS)** time is defined as the time from start date to the date of the first documentation of objective progression of disease or death due to any cause, whichever occurs first. PFS data will be censored on the date of the last adequate tumor assessment for subjects who do not have an event (progressive disease or death), for subjects who start a new anticancer therapy prior to an event or for subjects with an event after 2 or more missing tumor assessments. Subjects who do not have a baseline tumor assessment or who do not have any post-baseline tumor assessments will be censored on the treatment start date unless death occurred on or before the time of the second planned tumor assessment in which case the death will be considered an event.
- **Best Overall Response (BOR)** will be determined according to RECIST 1.1 (Appendix III). It is defined as the best response obtained among all tumor assessment visits after the date of first study drug administration until documented disease progression. The BOR rate is defined as the number of subjects with BOR was either confirmed CR or PR, relative to the number of subjects belonging to the study of interest.
- Only tumor assessments performed before the start of any further anticancer treatment will be considered in the assessment of BOR. Clinical deterioration will not be considered as documented disease progression.
- **Disease Control Rate (DCR)** is defined as a BOR of complete response (CR), PR or stable disease. Both CR and PR must be confirmed by repeat assessments performed no less than 4 weeks after the criteria for response are first met. DCR is the proportion of subjects with disease control.

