**Table 3**      **Outcome and Event Dates for PFS Analysis**

Scenario	Date of Event / Censoring	Outcome
No baseline assessment	Date of first study treatment	Censored a
Progression or death $\leq$ xx weeks after last tumor assessment or $\leq$ xx weeks after treatment start date, where xx is 16 weeks if the last assessment is at Screening or Cycle 3 (Evaluation Visit 1), 20 weeks if the last assessment is at Cycle 5 (Evaluation Visit 2), and 24 weeks if the last assessment is at Cycle 7 (Evaluation Visit 3) or later.	Date of progression or death	Event
Progression or death $>$ xx weeks after the last tumor assessment, where xx is 16 weeks if the last assessment is at Screening or Cycle 3 (Evaluation Visit 1), 20 weeks if the last assessment is at Cycle 5 (Evaluation Visit 2), and 24 weeks if the last assessment is at Cycle 7 (Evaluation Visit 3) or later.	Date of last adequate tumor assessment	Censored
No progression	Date of last adequate tumor assessment	Censored
Treatment discontinuation due to "Disease progression" without documented progression	Not applicable	Information collected on treatment discontinuation page is ignored since outcome should be derived based on documented progression only. General censoring rule is applied.
New anti-cancer therapy given	Date of last adequate tumor assessment before anti-cancer therapy is given	Censored

aIf the subject dies  $\leq$  16 weeks after treatment start date, the death is an event with date on death date.

Kaplan-Meier estimates (product-limit estimates) will be presented together with a summary of associated statistics (median survival time; 6- and 12-month survival rate estimates) including the corresponding two-sided 95% confidence intervals (CIs). The CI for the median will be calculated according to Brookmeyer and Crowley (1982), and CIs for the survival function estimates at the aforementioned time points will be derived using the log-log transformation according to Kalbfleisch and Prentice (1980) (conftype=loglog default option in SAS PROC LIFETEST). The estimate of the standard error will be computed using Greenwood's formula.

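### The PFS missed-scan limits in SAP Table 3 equal the nominal gap after one missed scan, so a progression at the next scheduled scan can be censored under a rule meant for two missed scans

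*SAP*

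**What the plan says.** Protocol Section 7.3 censors PFS at the last adequate tumour assessment "for subjects with an event after 2 or more missing tumor assessments". SAP Section 14.1 repeats the two-missed-assessments rule and explains it in brackets as "twice the scheduled time interval between two subsequent response assessments", adding that "this interval is 8 weeks through Cycle 7, and 12 weeks thereafter". SAP Section 7, which lists departures from the protocol's analyses, does not mention this rule, so Table 3 is meant to implement it.

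Table 3 counts a progression or death as an event up to and including a limit and censors it beyond that limit. The limit is 16 weeks when the last assessment was at Screening or Cycle 3, 20 weeks when it was at Cycle 5, and "24 weeks if the last assessment is at Cycle 7 (Evaluation Visit 3) or later". The event row also accepts an event within the same number of weeks from treatment start.

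On timing, footnote u of protocol Table 1 says "CT or MRI scans will be done for tumor assessments within 7 days prior to Day 1 of Cycles 3, 5 and 7", and every three cycles after that. Protocol Section 7.1.2 defines a cycle as 28 days and lets visits from Cycle 3 onward move by 3 days either way.

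**The concern.** A limit that separates one missed scan from two should lie between the two gaps. These limits lie exactly on the one-miss gap. Whether a documented progression counts then depends on whether the later scan fell a day later in its permitted window than the previous scan did in its own. A subject who missed one scan and otherwise kept to the schedule can lose the event and be censored at the earlier scan, against the rule in both documents. Turning progressions into earlier censorings tends to raise the Kaplan-Meier curve, from which SAP Section 14.1 reports the median and the 6- and 12-month rates.

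**Working it through.** **Inputs.** Cycle c Day 1 falls (c − 1) × 28 days after first dose. Scans are due at Cycles 3, 5, 7, 10, 13 and 16, that is at weeks 8, 16, 24, 36, 48 and 60. Each scan may be taken 0 to 7 days before Day 1, and Day 1 may move by up to 3 days. The documents do not say where in the windows scans actually fall, so any timing distribution is an assumption.

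**Reproducing the limits.** Each Table 3 limit is the sum of the next two scheduled intervals.

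| Last scan | Gap after one miss (weeks) | Gap after two misses (weeks) | Table 3 limit (weeks) |
|---|---|---|---|
| Treatment start (Screening scan) | 8 + 8 = 16 | 24 | 16 |
| Cycle 3 | 24 − 8 = 16 | 36 − 8 = 28 | 16 |
| Cycle 5 | 36 − 16 = 20 | 48 − 16 = 32 | 20 |
| Cycle 7 | 48 − 24 = 24 | 60 − 24 = 36 | 24 |

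The limits match the one-miss gaps in every row. For Cycle 5, the bracketed text read literally gives 2 × 8 = 16 weeks, whereas Table 3 uses 8 + 12 = 20.

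**Does the treatment-start anchor help?** Not for a last scan at Cycle 3 or later. The detecting scan is then at week 24, 36 or 48 from first dose, against limits of 16, 20 and 24 weeks. After a missed first scan it does help: an on-time Cycle 5 scan is at or before week 16.

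**Share over the limit, last scan at Cycle 3, 5 or 7, progression at the first scheduled scan after one miss.**

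- Independent, uniform scan days 0 to 7 before Day 1: there are 8 × 8 = 64 equally likely pairs, of which 8 are ties. The gap exceeds nominal in (64 − 8)/2 = 28 pairs, and 28/64 = 43.8%.
- With 3-day visit shifts added: the scan day takes 14 values with weights 1 to 7 and 7 to 1 out of 56. The tie probability is 280/3136 = 8.9%, so the share is (1 − 0.089)/2 = 45.5%.
- Leaving out Day 1 itself (1 to 7 days before): 42.9%, or 45.2% with visit shifts.
- Same position in the window each time: 0%.
- Half the subjects keep the same position: 0.5 × 43.8% = 22%.
- Later scan shifted 3 days early: 16%. Shifted 3 days late: 77%.

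**Missed first scan.** 0% if visits are on time. With 3-day visit shifts it is 6/56 = 11%, or 6% if Day 1 is left out. Weighting the four starting positions equally gives (0 + 3 × 43.8)/4 = 33% without visit shifts and (10.7 + 3 × 45.5)/4 = 37% with them; leaving out Day 1 lowers the first figure to 32%.

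**Room for a better limit.** Allowing 10 days early (7 + 3) and 3 days late, the longest one-miss gap is nominal + 13 days: 112 + 13 = 125, 140 + 13 = 153 and 168 + 13 = 181 days. The shortest two-miss gap to a scheduled scan is nominal − 13 days: 196 − 13 = 183, 224 − 13 = 211 and 252 − 13 = 239 days.

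**The case against.** A reader might infer that nearly half of all progressions after a single missed scan would be wrongly censored. The documents do not support that. The 44% to 46% needs independent, uniform scan timing, which they do not state. A site that books each subject at the same point in the window would produce no such censoring. The figure also leaves out the missed first scan, which the treatment-start anchor largely protects. It covers only progressions found at the next scheduled scan: protocol Section 7.3 allows extra scans on suspicion of progression, and one taken before the next due date stays inside the limit on nominal dates. The same holds for a death before the second due scan, while a death after that date does follow two missed scans.

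A reader might also infer a material upward bias in PFS. No missed-scan rate is given, so the size cannot be stated. SAP Section 9 treats all analyses as descriptive, the protocol plans about 24 subjects in Part IA, and the study ended early with one abbreviated final analysis. Subject-level tumour listings and a swimlane plot would show a borderline case.

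All of this stands and limits the weight of the point. It does not answer the mismatch itself: Table 3 can censor a progression after one missed scan, and the stated rule does not.

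**Conclusion.** The mismatch is real and follows from the schedule alone. For last scans at Cycle 3 or later, the 16-, 20- and 24-week limits are the nominal one-miss gaps, 12 weeks short of the two-miss gaps, and a gap one day over nominal censors the progression. How often this happens depends on scan timing: about 44% to 46% of progressions at the first scheduled scan after one miss under independent uniform timing, and 0% to 77% across the patterns tried, with shifts kept to the 3-day visit window. The number of subjects and the effect on the PFS curve are unknown. This is a correction worth making before database lock, to a descriptive secondary endpoint.

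**What to change.** Preferred: in SAP Section 14.1 and in both the event and censored rows of Table 3, apply the rule by counting missed scheduled scans. Treat a scan as missed only once its permitted window has closed without an adequate assessment, and state how a scan outside its window is assigned. This restores the stated rule for progressions and deaths alike and removes the 16-versus-20-week ambiguity after Cycle 5. It costs a short SAP revision and a slightly longer derivation.

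Alternative: for last scans at Cycle 3, Cycle 5, and Cycle 7 or later, set the limits to 18, 22 and 26 weeks (126, 154 and 182 days) in both rows, and amend the bracketed definition in Section 14.1 to include the window allowance. Under the permitted windows, no progression at the first scheduled scan after one miss would then be censored, and every progression first seen at a scheduled scan after two misses still would be. Adding only one week would leave 3% to 4% censored when visits also shift. The cost is that a death one to two weeks after a second missed scan becomes an event. For example, with a last scan at Cycle 3 and Cycles 5 and 7 missed, a death at 17 weeks would count. Counting missed scans avoids this.

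Under either option, keep the 16-week limit from treatment start and footnote a of Table 3 consistent with the rule for deaths by the second planned assessment. Add the treatment-start anchor to the censored row as well. At present a progression within 16 weeks of first dose can be more than 16 weeks after the screening scan, and so fit both rows.
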